2 INTRODUCTION: BACKGROUND INFORMATION AND SCIENTIFIC RATIONALE

2.1 Background Information

Early childhood caries (ECC) remains the most prevalent chronic childhood disease in the United States (Vargas et al., 1998; Poland & Hale, 2003; CDC, 2001) and poses a serious threat to child welfare, particularly among economically disadvantaged, underserved, and migrant children (Ramos-Gomez et al., 2007; DHF, 2006). National ECC prevalence (any decayed, extracted, or filled primary teeth (deft)) among 2–5 year olds was 23% in 2011–2012 (Dye et al., 2015). Mexican-Americans had double the ECC severity of non-Hispanic Whites (Wiener et al., 2015).

Since dental disease risk increases as a child's teeth erupt (ADA, 2014), brushing with fluoridated toothpaste (TP) (smear for children under 3 years old, pea-sized for those 3–6 years old) for 2 minutes twice daily (Creeth et al., 2009) can help prevent ECC. For 1- to 2-year old children, professional application of fluoride varnish (FV) over 2 years is efficacious (Weintraub et al., 2006; Gansky et al., 2007) and the standard of care for prevention. Powered toothbrushes can provide better plaque removal than manual toothbrushes (Yacoob et al. 2014), but may also have a short-term novelty effect. Research participants using powered toothbrushes may also experience a Hawthorne effect from knowing they are in a research study. Both the novelty and Hawthorne effects have been reported to abate after 12 weeks among college students in a randomized controlled trial (RCT) evaluating plaque levels (McCracken et al. 2000).

Types of Rewards. Incentives are a common component of health promotion programs. Recognizing the important role that incentives can play, NIH has placed the evaluation of incentives on health-related behaviors among its highest priority areas for health economics research (NIH, NOT-OD-16-025, 2015).

Lottery prizes (a type of monetary incentive) have been more successful than non-monetary incentives for encouraging more physical activity (Wing et al., 1996), smoking

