3.2.2 Secondary

Intermediate toothbrushing performance measures are as follows:

- Mean of the number of qualifying half-day toothbrushing episodes per week, through 1 month for short-term effects
- Mean of the number of qualifying half-day toothbrushing episodes per week, through the Month 3 visit for mid-term effects after any novelty effect would be expected to end,
- Mean of the number of qualifying half-day toothbrushing episodes per week, from Month 6 visit to Month 12 visit for longer-term effects

For the outcomes listed above, the minimum qualifying length of time is 1 minute.

Additional secondary oral health measures will be ascertained:

- Debris Index of the Simplified Oral Hygiene Index for Maxillary Incisors (OHI-MIS) to measure plaque on primary maxillary incisor facial (labial) tooth surfaces at Month 6 and Month 12 visits (mean of 4 ordinal scores)
- TP pump weight change (grams) at Month 6 and Month 12 visits
- Binary measure of Association of State and Territorial Dental Directors Basic Screening Survey (ASTDD BSS) untreated caries status ($dt>0$) at Month 6 and Month 12 visits
- Binary measure of ASTDD BSS caries experience status ($dmft>0$) at Month 6 and Month 12 visits; m is missing due to caries only
- Binary measure of ASTDD BSS severe caries ($dmft 4+$) status at Month 6 and Month 12 visits; m is missing due to caries only
- Binary measure of a dental visit in the past 12 months, obtained through EHS ChildPlus database which records annual dental visit and other required health screenings

To assess potential mediation effects of beliefs (behavioral, normative, and control) on intermediate outcomes (intentions, salience, and habit) and primary outcome (toothbrushing performance), the aforementioned primary and secondary outcome measures will be assessed. Behavioral, normative, and control beliefs will be collected via the BRFQ at each study visit (see Section 8.3). Intentions, salience, and habit will be collected with components of the BRFQ (e.g. intentions to brush child's teeth in the next 6 months, preventive habits for one's self and for one's child, age started brushing study child's teeth.).

To estimate the short- and long-term cost effectiveness and return on investment of rewards in improving parent/caregiver behaviors and children's oral health, net costs will be ascertained (as detailed in Section 12.4).

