In the Delayed Monetary Reward Control group, participants will receive feedback on their toothbrushing performance during the first 12 months of the trial. After the Month 12 follow-up visit, the Control group participants will have the option to participate in a delayed 6-month extension by being randomized to one of two groups to earn the same expected monetary rewards the intervention group was eligible to earn through Month 6; both Control groups will have weekly drawings (as in the intervention group though 6 months), but one Control group will be randomized into drawing results shared weekly (as in the intervention group through 6 months), while the other randomized Control group will have the 13 weekly drawing results only shared quarterly, with equal reward amounts and the same probabilities for high and low thresholds.

Toothbrushing performance will be ascertained via Philips Sonicare for Kids (S4K) powered toothbrushes and brush heads, which will be synced with a custom BEECON study version of their existing S4K smartphone application. Data to be transmitted includes toothbrushing start time, toothbrushing duration, application start time, and whether toothbrushing was conducted with the application open or without the application (offline).

SMS text message notifications will be sent via Twilio and REDCap to remind participants to sync the powered toothbrush to the smartphone app. Further, all study participants will be sent weekly SMS text messages with feedback on toothbrushing progress, and, if in the intervention group, the incentives earned.

Additionally, participants will undergo study visits every 3 months. At screening and Month 6, 12, and 18 visits the participating child will receive an ASTDD BSS dental screening after parents/caregivers provide a brief child medical history, and a OHI-MIS plaque score will be determined. Participants in each group will be provided a new TP pump at the Month 6 and Month 12 visits and 1 new brush head at each study visit (every 3 months). Questionnaires will be configured in REDCap.

Four focus group discussions (FGDs) of trial participants will be conducted after the Month 6 visit, and two FGDs of intervention arm participants will be conducted after the Month 12 visit. Participants will be chosen based on study performance (e.g., above and below high and low thresholds of toothbrushing adherence).

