5 STUDY ENROLLMENT AND WITHDRAWAL

5.1 Subject Inclusion Criteria

Child

To be eligible to participate in this study, a child must meet all of the following criteria, to be verified during a screening visit:

- at least 6 months old but less than 4 years (48 months).
- at least 2 fully erupted teeth.
- enrolled in, or waitlisted for, one of the participating Los Angeles County EHS or affiliated day care center or area clinic programs.

Parent/caregiver

To be eligible to participate in this study, a parent/caregiver must meet all of the following criteria, to be verified during a screening visit:

- Provide signed and dated informed consent form in English or Spanish.
- Agree to comply with all study procedures and be available for the duration of the study.
- Aged 18 and older.
- Speak either English or Spanish and self-reported ability to read and write either English or Spanish.
- Be a parent or caregiver of a child at least 6 months old but less than 4 years (48 months), with at least 2 fully erupted teeth and enrolled in, or waitlisted for, one of the participating Los Angeles County EHS or affiliated day care center or area clinic programs.
- Not be planning to move residence for the next 18 months outside the greater Los Angeles area.
- Own a smartphone with the Google Play or iTunes store and be willing to download and install the smart powered TB app at the Screening visit and keep it installed for the duration of the project. [If the app cannot be properly installed by the baseline visit, the participant will not be randomized.]
- Be willing to be contacted via text-messaging (SMS) for study related notifications, such as incentives earned or reminders to sync the TB.

Stakeholder

To be eligible to participate in the stakeholder interviews, a staff member must meet all of the following criteria:

- Be a staff member at a participating study site (e.g. EHS or affiliated day care center).
- Verbally agree to participate after being provided a study information sheet.

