5.2 Subject Exclusion Criteria

Child

A child who meets any of the following criteria will be excluded from participation in this study:

- Known allergic reaction to components of the study product(s).

- Uncooperative or behaviorally unsuited (assessed during a TB prophylaxis, ASTDD BSS caries screening, and photograph of maxillary incisors at the screening visit).
- More than 2 crowns on maxillary incisor teeth (#D, E, F, G, or equivalently #52, 51, 61, 62).
- Participated in the pilot trial.
- A sibling of a child enrolled in the study (the family's oldest child in the eligible age range will be the study child).
- Enrolled in foster care.
- Anything else that would place him/her at increased health risk or preclude the individual's full compliance with or completion of the study.

Parent/caregiver

A parent/caregiver who meets any of the following will be excluded from participation in the study:

- Participated in the pilot trial.
- Unable or unwilling to install and use the smart powered TB app during the run-in period.

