7.1.1 Screening Visit (Visit 1, T = business day -10)

- Explain purpose and procedures of study to prospective parent/caregiver participant. Verify inclusion/exclusion criteria.
- Obtain and document consent from subject on study consent form electronically with DocuSign.
- Study staff download app on parent's/caregiver's smartphone and sync the TB to his/her smartphone. Walk parent through the app. Explain how to sync.
- Administer CAPI questionnaire to parent/caregiver.
- Record medical history and perform ASTDD BSS dental screening on child participant's teeth (by blinded dental provider); record decay and assess treatment urgency. Children with urgent treatment needs will be referred with a warm handoff to staff at the corresponding dental clinic.
- Apply plaque disclosing agent to child's teeth (by blinded dental provider).
- Take extraoral photograph(s) of the facial surfaces of child's anterior teeth.
- Give the family the Oral Hygiene Kit, which includes the smart powered toothbrush and fluoride TP pump. Attach label with child's name.
- Instruct the parent/caregiver on how to use the TP pump to show the proper amount of TP, and how to brush the child's teeth. Have the parent brush off the child's plaque disclosing solution.
- Apply FV to the child's teeth (by dental provider).
- Have the parent/caregiver watch the standardized Anticipatory Guidance presentation on a tablet.

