12.4 Final Analysis Plan

Intent-to-treat (ITT) analyses standard in incentive based behavioral economics studies will be utilized (e.g. Halpern *et al.* 2015, Patel *et al.* 2016). Generalized linear mixed models (GLMMs) will be used to compare primary and secondary outcomes over time between groups. GLMMs make fewer missing data assumptions than other methods, which assume missing data are missing completely at random. Identity link will be used for numeric (interval) outcomes (e.g., mean number of qualifying half-day toothbrushing episodes per week, through Month 6 visit; mean OHI-MIS plaque score; and TP pump weight change). The group x time interaction will also be assessed; short-term effects will be assessed for 1 month of the intervention, mid-term effects after the novelty effect of powered toothbrushing usually ends for the Month 3 Visit, and long-term effects for the Month 6 Visit (primary outcome), as well as, maintenance of behavior after removing the incentives for the Month 12 Visit. Recent, powerful Precision Medicine methods which do not inflate Type I error will be used to detect heterogeneity of treatment effects by groups of participants based on baseline characteristics (e.g., Lazar *et al.* 2013). Multiple imputation using chained equations (MICE) for arbitrary missingness patterns (Raghunathan *et al.* 2001; van Buuren 2007) will be used for sensitivity analyses. Supplemental analyses will also explore: a) trajectories of mean number of qualifying half-day brushing episodes per week over time; as well as b1) variability in morning brushing times, b2) variability in evening brushing times, and c) variability in weekday versus weekend brushing times associated with mean number of qualifying half-day brushing episodes, OHI-MIS plaque scores, and ASTDD BSS caries screening measures.

To examine potential impact of timing of drawing reward communication time, GLMM analyses as above will be performed comparing the weekly and quarterly drawing result communication arms for primary and secondary outcome data from Month 12 to Month 18.

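### Caries experience and severe caries are defined as status at Months 6 and 12 with no stated role for the screening examination, so children already positive before randomisation dilute the comparison

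*Combined protocol and SAP*

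**What the plan says.** Section 3.2.2 places three binary caries measures among the additional oral health outcomes, each taken at Months 6 and 12: untreated decay (dt>0), a "Binary measure of ASTDD BSS caries experience status" (dmft>0), and severe caries (dmft of 4 or more). In the last two, missing teeth count only if lost to caries.

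The baseline value exists. Section 4 states: "At screening and Month 6, 12, and 18 visits the participating child will receive an ASTDD BSS dental screening". Section 7.1.1 lists the same examination among the screening procedures: "Record medical history and perform ASTDD BSS dental screening on child".

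Children with caries can enter. The only related exclusion in section 5.2 is "More than 2 crowns on maxillary incisor teeth".

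Section 12.4 applies generalized linear mixed models to primary and secondary outcomes over time and plans a group-by-time term. The times it lists are 1 month and Months 3, 6 and 12. On the link it says "Identity link will be used for numeric (interval) outcomes"; it names none for binary outcomes. It mentions no caries covariate, caries-free subset or new-onset definition.

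**The concern.** dmft counts decayed teeth, filled teeth and teeth lost to caries. Once a child has dmft>0, treatment does not reverse it, and the same holds for dmft of 4 or more. A child who meets the definition at screening therefore meets it at Months 6 and 12 whatever the reward does. Such children add the same expected share of positives to both arms. That moves the risk ratio towards 1, shrinks the risk difference and adds variance.

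Section 4 names caries screening status among the outcomes on which reward effects are to be determined, and section 12.4 carries dental health events into the cost-effectiveness work. A diluted ratio could be read as little preventive effect when part of the dilution is disease that predates randomisation.

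Untreated decay (dt>0) is different: it can resolve with treatment, so children positive at screening remain informative.

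**Working it through.** **Plan's own figure.** Section 12.2 gives 84% power for the brushing outcome with 91 per arm, a difference of 2.65 and SD 6.0. SE = 6.0 × √(2/91) = 0.890; 2.65/0.890 − 1.96 = 1.02; Φ(1.02) = 84.6% (84.2% with the t distribution). Then 91/0.75 = 121.3, so 122 per arm and 244 dyads. Both reproduce. No power is stated for any caries outcome.

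**Inputs.**
- n = 91 per arm and two-sided alpha 0.05: section 12.2.
- Baseline prevalence b: not given for trial children. Section 2.1 says that prevalence among those aged 2–5 "year olds was 23% in 2011–2012" nationally. Assumed 23%, range 5-46%.
- Twelve-month control incidence i among caries-free children: not given. Assumed 10-30%.
- Risk ratio RR for new caries: not given. Assumed 0.5 or 0.7.
- dmft>0 does not revert.

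**Formulas.** Status at the visit: p = b + (1 − b) × incidence, with n = 91. New onset: i against i × RR, with n = 91 × (1 − b). Power = Φ{[d − 1.96 √(2p̄(1 − p̄)/n)] / √[(p1(1 − p1) + p2(1 − p2))/n]}, where d is the difference and p̄ the mean of the two proportions.

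**Central example (b = 23%, new caries 20% against 10%).**
- Status: control 0.23 + 0.77 × 0.20 = 38.4%; reward 0.23 + 0.77 × 0.10 = 30.7%. Ratio 0.80, difference 7.7 points. Power = Φ[(0.077 − 0.138)/0.0703] = 19%.
- New onset: 20% against 10% in 91 × 0.77 ≈ 70 per arm. Ratio 0.50, difference 10 points. Power = Φ[(0.100 − 0.118)/0.0597] = 38%.
- Relative loss: 1 − 0.192/0.380 = 49%. For 80% power, about 598 per arm are needed on status, against about 259 per arm (counting all children) on new onset.

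**Range at i = 20%** (power on status → power on new onset, relative loss).

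| Baseline prevalence | RR 0.5 | RR 0.7 |
|---|---|---|
| 5% | 37% → 45% (19%) | 15% → 18% (15%) |
| 10% | 30% → 43% (31%) | 13% → 17% (25%) |
| 23% | 19% → 38% (49%) | 10% → 15% (39%) |
| 35% | 14% → 33% (58%) | 8% → 14% (45%) |
| 46% | 11% → 28% (61%) | 6% → 12% (47%) |

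Over the full grid (i of 10, 15, 20 and 30%), the relative loss runs from 11% to 64%, or 2 to 24 percentage points. The highest power for new onset is about 66%. Simulation with 40,000 runs per scenario gives the same range of relative loss.

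**Does adjusting for screening status work?** Take 70 caries-free children per arm with 14 and 7 new cases, plus 21 per arm who are positive throughout.
- Caries-free subset: log odds ratio = ln[(7/63)/(14/56)] = −0.811; SE = √(1/7 + 1/63 + 1/14 + 1/56) = 0.498; p = 0.103.
- All 182 children, logistic model with screening status as covariate: treatment log odds ratio −0.811, SE 0.498, p = 0.103. Only the coefficient for screening status diverges.
- All children, no covariate: 28/91 against 35/91, ln[(28/63)/(35/56)] = −0.341; SE = √(1/28 + 1/63 + 1/35 + 1/56) = 0.313. The ratio of estimate to SE falls from 1.63 to 1.09.

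**The case against.** The strongest reply is that section 12.4 does not commit to an unadjusted comparison at the visit. It compares outcomes over time, plans a group-by-time term, and does not say whether screening is one of the times. In the central example, a simulated comparison of change from screening in all children had 37% power, against 38% for new onset. (This compared proportions; it was not a fitted mixed model.) That part stands: the text leaves the baseline unspecified rather than choosing to ignore it. But the times it lists start at 1 month, so the text cannot be relied on to bring the screening value in.

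It is also true that randomisation keeps the comparison valid, that the sample size rests on one brushing outcome, and that status at the visit matches the wording of the aim in section 4. These points limit the weight of the comment but do not remove the dilution.

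Three stronger readings are tempting and not supported.
- A reader might take half the power as the established loss. The 23% is national and for ages 2 to 5. Enrolment from 6 months could make trial prevalence lower, and the high-risk population could make it higher. No document supports a halving of caries.
- A reader might infer that the outcome measures mostly caries from before randomisation. In the central example that share of control-arm positives is 23/38.4 = 60%, but at 10% baseline prevalence it is 10/28 = 36%.
- A reader might infer that adjusting for screening status must fail because children positive at screening predict the outcome perfectly. The check above shows that the treatment estimate is finite and equals that of the caries-free subset.

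**Conclusion.** The point holds as a gap in the specification with a real but uncertain cost. As written, dmft>0 and dmft of 4 or more include children whose result is fixed before randomisation, and the screening value that would deal with this is collected but given no role.

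Under the assumptions above, the relative loss of power is roughly 10-65%. It is about half at 23% baseline prevalence with new caries of 20% against 10%, where the risk ratio reads 0.80 instead of 0.50. With RR 0.7 in the same setting, the gain from the change is only about 6 percentage points. The calculation is for dmft>0 at 12 months. The mechanism carries over to dmft of 4 or more, but its baseline prevalence is not given; it cannot exceed that of dmft>0, and the dilution may be small.

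Type I error is not affected. The change does not turn these into adequately powered outcomes: every scenario stays below 80% either way. The primary brushing result is untouched. The change is worth making because it uses data already collected.

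**What to change.** In sections 3.2.2 and 12.4:
- Define caries experience as new dmft>0 among children with dmft=0 at screening, and severe caries as new dmft of 4 or more among children below 4 at screening, with a logit link. Alternatively, keep all children and adjust for the matching screening status, noting that its own coefficient will diverge while the treatment estimate does not.
- For dt>0, keep all children and adjust for screening status.
- Name the link for binary outcomes and say whether screening is a time point in the mixed model.

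The cost is wording; no new data are needed. The new-onset version analyses fewer children (about 70 instead of 91 per arm at 23% baseline prevalence), and its result is conditional on being caries-free, or below 4, at screening. Prevalence at each visit can still be reported descriptively. Settle the choice before unblinding, because choosing between status and new onset afterwards would be driven by the data.

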4 STUDY DESIGN

We will conduct a stratified RCT testing the impact of monetary rewards on ECC preventive behaviors and oral health. Eligible child-parent/caregiver participant dyads will be consented, enrolled, and, following a 2 week run-in, randomized within strata and permuted blocks in equal allocation to one of two groups: 1) Monetary Rewards or 2) Delayed Reward Control. Strata will be based on site and smartphone operating system. The intervention will be offered for 6 months, and children (ages 6 months through <48 months) will be followed for 12 months to determine reward effects on dental visit attendance, toothbrushing, fluoride TP use, OHI-MIS plaque score , and caries screening status. Results will inform researchers and public health practitioners on the longer-term maintenance of behavioral changes and oral health screening status following removal of the rewards.

The study population will be predominantly low income Hispanics/Latinos who are parents/caregivers with children enrolled in, or waitlisted for, one of the participating Los Angeles County EHS or affiliated day care center programs. After enrollment parents/caregivers will use powered toothbrushes for a 2 week run-in to ensure their technology works and they are willing to follow study procedures; after the enrollment visit and run-in, randomization will occur at a separate visit. Participants who are unable to provide data during the run-in period will not be randomized or continue in the study.

Participants in the Monetary Reward group will be eligible to earn one of two incentive amounts every week for the first 6 months of the trial. A participant who meets a low or high threshold will earn entry in that week's drawing for financial incentives (See Section 6.1 for additional details).

In the Delayed Monetary Reward Control group, participants will receive feedback on their toothbrushing performance during the first 12 months of the trial. After the Month 12 follow-up visit, the Control group participants will have the option to participate in a delayed 6-month extension by being randomized to one of two groups to earn the same expected monetary rewards the intervention group was eligible to earn through Month 6; both Control groups will have weekly drawings (as in the intervention group though 6 months), but one Control group will be randomized into drawing results shared weekly (as in the intervention group through 6 months), while the other randomized Control group will have the 13 weekly drawing results only shared quarterly, with equal reward amounts and the same probabilities for high and low thresholds.

Toothbrushing performance will be ascertained via Philips Sonicare for Kids (S4K) powered toothbrushes and brush heads, which will be synced with a custom BEECON study version of their existing S4K smartphone application. Data to be transmitted includes toothbrushing start time, toothbrushing duration, application start time, and whether toothbrushing was conducted with the application open or without the application (offline).

SMS text message notifications will be sent via Twilio and REDCap to remind participants to sync the powered toothbrush to the smartphone app. Further, all study participants will be sent weekly SMS text messages with feedback on toothbrushing progress, and, if in the intervention group, the incentives earned.

Additionally, participants will undergo study visits every 3 months. At screening and Month 6, 12, and 18 visits the participating child will receive an ASTDD BSS dental screening after parents/caregivers provide a brief child medical history, and a OHI-MIS plaque score will be determined. Participants in each group will be provided a new TP pump at the Month 6 and Month 12 visits and 1 new brush head at each study visit (every 3 months). Questionnaires will be configured in REDCap.

Four focus group discussions (FGDs) of trial participants will be conducted after the Month 6 visit, and two FGDs of intervention arm participants will be conducted after the Month 12 visit. Participants will be chosen based on study performance (e.g., above and below high and low thresholds of toothbrushing adherence).

Stakeholder interviews (6-12) with EHS and affiliated day care center staff will be conducted after the Month 6 visit.

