8.6 Dental Visit Attendance

For children enrolled at an EHS, preventive dental visit attendance of participating children will be ascertained through dental exam data from Head Start's ChildPlus Management Software health module at baseline and the Month 12 follow-up. In addition, for all children, parents will be asked about the date of the last dental visit within the baseline and Month 12 follow-up questionnaire.

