12.2 Sample Size Considerations

With 2 parallel groups, the sample size calculation was conservatively conducted for one continuous outcome using short-term pilot data; the mean number of qualifying brushing episodes in a half-day window per week through 6 weeks was 5.5 with a standard deviation (SD) of 4.8 for a coefficient of variation (CV) of 0.87. To be more conservative, a SD 25% larger (i.e. 6.0) was used. The mean percent of qualifying brushing episodes (out of 14 half-days per week) was 63% with a SD=32% for a CV=0.514. A sample size of 91 in each group is estimated to have 84% power to detect a difference in means of 2.65 with a common SD of 6.0 using a two group t-test with 2-sided alpha=0.05.

In addition, a sample size of 91 in each group was estimated to have 85% power to detect a 1.25-fold change in means (expected ratio) between intervention and control with the larger (more conservative) CV=0.525 using a two group 2-sided t-test with alpha=0.05. With a CV=0.567 and a 1.25-fold change or a CV=0.695 and a 1.30-fold change, n=91 per group is still estimated to have 80% power.

Assuming 75% retention over 12 months, a total of 244 parent-child dyads (N=488) will need to be enrolled. (Retention was 85% over 24 months in the team's recently completed glass ionomer sealant and fluoride varnish trial (GIFT) in a similar

population. Retention was 75% over 2 months in the BEECON pilot trial, but retention procedures have been added including a 2 week run-in to eliminate people enrolling only for the powered toothbrush.)

Sample sizes for semi-structured interviews and focus group discussions are based on prior experience. Focus group discussions with a total of 40 parent/caregiver participants are expected to reach saturation, but it is possible an additional focus group discussion will be needed to reach saturation.

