To investigate the behavioral economics mechanisms through which behavior change outcomes may have operated, **mediation analyses** will be conducted with the measures of risk preferences (i.e., for the presence of prospect theory tendencies), time preferences (i.e., for the presence of present bias), and forgetfulness (i.e., for attention). Each of these factors will be investigated in separate models to assess the extent the particular underlying construct lies within the pathway toward toothbrushing behavior change (i.e., by reducing the estimate of the ITT main effect).

In addition, because parents and children with different backgrounds (e.g., child's age, parent's/caregiver's education) and behavioral, normative, and control beliefs may respond differently to the incentives given, heterogeneity of treatment effect analyses will be conducted to identify groups influenced by the intervention. For example, the UH2 pilot (White *et al.* 2020) suggested the intervention on toothbrushing frequency may vary by child age (<24mo vs \geq 24mo). The results of these analyses will also inform the sampling frame for the parent FGDs so that important dimensions of diversity can be represented.

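### Section 12.4 specifies no child-age or baseline term in the between-arm models for dental visits and caries, although these variables are collected before randomisation

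*Combined protocol and SAP*

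**What the plan says.** - **Outcomes.** Section 3.2.2 lists the dental-visit outcome as "Binary measure of a dental visit in the past 12 months, obtained through EHS ChildPlus database". It also lists three binary Basic Screening Survey (BSS) caries measures at Month 6 and Month 12: untreated caries, caries experience and severe caries. All are secondary.
- **Population.** Section 4 states that "children (ages 6 months through <48 months) will be followed for 12 months to determine reward effects on dental visit attendance". Section 5.1 admits children with as few as two erupted teeth.
- **Age as a predictor.** Section 2.1 says "Since dental disease risk increases as a child's teeth erupt". Section 2.2 cites guidance that dental attendance should start at about age one or soon after the first tooth.
- **Baseline data.** Under 8.6, ChildPlus dental records are taken at baseline and Month 12 for Early Head Start (EHS) children. For all children, "parents will be asked about the date of the last dental visit within the baseline and Month 12 follow-up questionnaire". Sections 4 and 7.1.1 place a BSS examination at screening. Section 7.1.2 lists the questionnaire ahead of the randomisation step.
- **Randomisation.** Strata are site and phone type (5.4.1). Age is not a stratum.
- **Analysis.** Section 12.4 uses mixed models over time for all outcomes. It gives a link for numeric outcomes but none for binary ones, and it lists no covariates. Child age comes in only because "parents and children with different backgrounds (e.g., child's age, parent's/caregiver's education" may respond differently, which is a question of effect heterogeneity.

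**The concern.** The children range from infants with two teeth to children almost four years old. On the protocol's own account, age should predict both dental attendance and caries, and each outcome also has a recorded pre-randomisation counterpart. A between-arm model that omits strong predictors of a binary outcome has less power than one that includes them. These outcomes have no stated power, so any precision available at no cost is worth taking.

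There is also a matter of discretion. With no covariates named, whether to adjust, and for what, could be decided after the data are seen.

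**Working it through.** **1. The plan's own figures.** Section 12.2 covers toothbrushing only: "A sample size of 91 in each group is estimated to have 84% power to detect a difference in means of 2.65". The test is two-sided at the 5% level, and the SD is taken as 6.0.

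- Standardised difference: 2.65 / (6.0 × √(2/91)) = 2.979.
- Power: Φ(2.979 − 1.96) = 84.6% by normal approximation, and 84.2% by noncentral t. The stated 84% reproduces.
- The second statement, "85% power to detect a 1.25-fold change in means (expected ratio) between intervention and control" at a CV of 0.525, gives 85.9% on the log scale.
- Enrolment: 182 / 0.75 = 243, against a stated 244.

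None of these figures concerns dental visits or caries. The documents give no event rate, effect size or predictor strength for those outcomes, so everything below rests on assumptions.

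**2. General size of the gain.** Let R² be the share of outcome variance that the covariates explain. Then, approximately, adjusted power = Φ[(z_power + 1.96)/√(1 − R²) − 1.96]. For example, with unadjusted power of 60% and R² = 0.25: (0.253 + 1.96)/0.866 − 1.96 = 0.596, and Φ(0.596) = 72.4%, a gain of 12.4 points.

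| Unadjusted power | R² 0.05 | R² 0.15 | R² 0.25 | R² 0.30 |
|---|---|---|---|---|
| 50% | +2.0 | +6.6 | +11.9 | +14.9 |
| 60% | +2.2 | +7.0 | +12.4 | +15.3 |
| 80% | +2.0 | +6.0 | +9.9 | +11.8 |

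**3. Dental visit, logistic simulation.** Assumptions: 91 per arm, 60% of controls with a visit, age uniform on 0.5 to 4 years, about 50% with a baseline visit, and a Wald test of arm with and without the covariates.

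| Baseline-visit OR; age OR per year | Power at arm OR 2.5, unadjusted → adjusted | Gain over repeated runs, arm OR 2.5 |
|---|---|---|
| 2; none | 77% → 78% | about 1 |
| 4; 1.5 | 66% → 72% | about 6 to 7 |
| 8; 2.0 | 54% → 66% | about 12 to 14 |

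At an arm odds ratio of 1.5, the gain over the same three settings is only about 0 to 4 points, from power of roughly 15 to 25%. At 1.3 it is about 0 to 1 point.

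A separate simulation with visit rates of about 54% and 71% gives a similar pattern: 65.3% → 66.9% (R² about 0.05), 70.1% → 75.2% (0.16) and 68.4% → 79.6% (0.27).

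**4. Caries.**

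- Age alone, among children caries-free at screening (70 per arm, 20% incidence, arm OR 0.35): 48% → 49% at an age OR of 1.5 per year, and 42% → 49% at 3.0. The plan makes no such restriction.
- Age alone, all children (91 per arm): 46.1% → 47.5% and 46.4% → 48.8%.
- Age plus a strong baseline caries status (coefficient 2.5, so OR e^2.5 = 12.2; R² 0.27): 50.1% → 62.6%.

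Most of the useful gain for caries therefore comes from the baseline examination, not from age.

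**5. Null behaviour.** With no arm effect, rejection is 4.9% unadjusted and 5.0% adjusted in one check, and about 4 to 6% across the dental-visit settings. Both analyses are valid.

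**The case against.** **Baseline may already be in the model.** A mixed model over time could carry the baseline record as a repeated response, so the non-use of baseline is inferred from silence. That stands: the accurate statement is that its use is not specified. The text does not favour that reading, however. Dental visits have a single post-baseline assessment, the caries measures are defined at Months 6 and 12, and the time points named in 12.4 do not include baseline. No reading puts age into the between-arm comparison as a covariate.

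**The effect may be small.** Rewards depend on toothbrushing, not on seeing a dentist (3.2.1, 6.1), so nothing supports a dental-visit odds ratio as large as 2.5. This also stands. With a modest effect, power is low with or without adjustment.

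**Stronger readings that the documents do not support.**

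- A reader might infer that the unadjusted comparison is biased. It is not. An unadjusted odds ratio closer to 1 reflects non-collapsibility, which is a different estimand, and chance age imbalance under randomisation is already reflected in the standard error.
- A reader might infer that about 12 points of power are lost on every binary outcome. For dental visits that needs strong predictors and a large effect. For caries it needs strong baseline caries status.
- A reader might infer that the plan ignores age. It uses age, but only to look for effect heterogeneity.

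**Conclusion.** The point holds as a no-cost improvement to secondary analyses. Section 12.4 specifies no baseline or age term for the dental-visit and BSS caries comparisons, although all the variables needed are collected before randomisation. The benefit is precision, plus removal of discretion over the choice of covariates.

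Its size cannot be derived from the documents. The power gains of about 1 to 14 points (dental visits, assumed odds ratio 2.5), 0 to 4 points (odds ratio 1.5), 1 to 7 points (caries, age alone) and about 12 points (caries, strong baseline status added) all rest on assumed event rates and predictor strengths. They should be quoted as a range with those assumptions. The primary toothbrushing analysis and the 244 dyads are untouched.

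**What to change.** In 12.4, before arm assignments are revealed to the analysts:

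1. Fit the Month 12 dental-visit outcome by logistic regression on arm, child age at randomisation (continuous) and baseline dental visit (yes/no). Take the baseline value from the same source as the outcome, and name that source. Section 3.2.2 relies on ChildPlus, which 8.6 limits to EHS children; only parent report covers everyone. For infants under 12 months, a visit in the past year simply means any visit so far, which is a further reason to keep age in the model.
2. Fit each BSS caries outcome on arm, child age at randomisation and the same BSS measure at screening. Caries experience should rarely revert, and severe caries may be rare, so name a fallback such as penalised likelihood in case the baseline term separates.
3. Report the standardised (marginal) risk difference with its interval beside the odds ratio, so that the arm contrast stays interpretable.
4. State how missing baseline values are handled.

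The cost is SAP wording only: no new data, visits or participants.
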